13.1 Regulatory and ethical compliance

This clinical study was designed and shall be implemented, executed and reported in accordance with the ICH Harmonized Tripartite Guidelines for Good Clinical Practice, with applicable local regulations, and with the ethical principles laid down in the Declaration of Helsinki.

13.2 Responsibilities of the investigator and IRB/IEC

Before initiating a trial, the investigator/institution must obtain approval/favorable opinion from the Institutional Review Board/Independent Ethics Committee (IRB/IEC) for the trial protocol, written ICF, consent form updates, participant recruitment procedures (e.g. advertisements) and any other written information to be provided to participants. Prior to study start, the investigator is required to sign a protocol signature page confirming his/her agreement to conduct the study in accordance with these documents and all of the instructions and procedures found in this protocol and to give access to all relevant data and records to Novartis monitors, auditors, Novartis Quality Assurance representatives, designated agents of Novartis, IRBs/IECs, and regulatory authorities as required. If an inspection of the clinical site is requested by a regulatory authority, the investigator must inform Novartis immediately that this request has been made.

13.3 Publication of study protocol and results

The protocol will be registered in a publicly accessible database such as clinicaltrials.gov. In addition, after study completion (defined as last patient last visit) and finalization of the study report the results of this trial will be submitted for publication and posted in a publicly accessible database of clinical trial results, such as the Novartis clinical trial results website and all required health authority websites (e.g. clinicaltrials.gov) .

For details on the Novartis publication policy including authorship criteria, please refer to the Novartis publication policy training materials that were provided to you at the trial investigator meetings.

13.4 Quality Control and Quality Assurance

Novartis maintains a robust Quality Management System (QMS) that includes all activities involved in quality assurance and quality control, to ensure compliance with written Standard Operating Procedures as well as applicable global/local GCP regulations and ICH Guidelines.

Audits of investigator sites, vendors, and Novartis systems are performed by auditors, independent from those involved in conducting, monitoring or performing quality control of the clinical trial. The clinical audit process uses a knowledge/risk-based approach.

Audits are conducted to assess GCP compliance with global and local regulatory requirements, protocols and internal SOPs, and are performed according to written Novartis processes.

13.5 Participant Engagement

The following participant engagement initiatives are included in this study and will be provided, as available, for distribution to study participants at the timepoints indicated. If compliance is impacted by cultural norms or local laws and regulations, sites may discuss modifications to these requirements with Novartis.

- Thank You letter
- Plain language trial summary - after CSR publication
- Trial Feedback Questionnaires (TFQ)

14 Protocol adherence

This protocol defines the study objectives, the study procedures and the data to be collected on study participants. Additional assessments required to ensure safety of participants should be administered as deemed necessary on a case by case basis. Under no circumstances including incidental collection is an investigator allowed to collect additional data or conduct any additional procedures for any purpose involving any investigational drugs under the protocol, other than the purpose of the study. If despite this interdiction prohibition, data, information, observation would be incidentally collected, the investigator shall immediately disclose it to Novartis and not use it for any purpose other than the study, except for the appropriate monitoring on study participants.

Investigators ascertain they will apply due diligence to avoid protocol deviations. If an investigator feels a protocol deviation would improve the conduct of the study this must be considered a protocol amendment, and unless such an amendment is agreed upon by Novartis and approved by the IRB/IEC and Health Authorities, where required, it cannot be implemented.

16.1 Appendix 1: Liver event and laboratory trigger definitions & follow-up requirements

Tables below provide the clinically notable liver function test results and the required actions.

When the laboratory abnormality is deemed clinically significant, AEs must be reported.

Clinical symptoms with a diagnosis must be reported as AEs.

Table 16-1 Follow up requirements for liver laboratory triggers

ALT or AST	TBL	Liver Symptoms	Action
ALT/AST increase without bilirubin increase:			
If normal at baseline: ALT/AST > 3 x ULN	Normal; For participants with Gilbert's syndrome: No clinically significant change in baseline TBL	None	
 No change to study treatment Measure ALT, AST, ALP, GGT, TBIL, INR, albumin, CK, and GLDH in 48-72 hours. Follow-up for symptoms/etiology to establish causality
If elevated at baseline: ALT/AST > 2 x baseline			
If normal at baseline: ALT/AST > 5 x ULN for more than two weeks	Normal; For participants with Gilbert's syndrome: No clinically significant change in baseline TBL	None	
If elevated at baseline: ALT/AST > 3 x baseline for more than two weeks			
 Interrupt study drug Measure ALT, AST, ALP, GGT, TBIL, INR, albumin, CK, and GLDH in 48-72 hours. Follow-up for symptoms/etiology to establish causality.
If normal at baseline: ALT/AST > 8 x ULN	Normal	None	
ALT/AST increase with bilirubin increase:			
If normal at baseline: ALT/AST > 3 x ULN	TBL > 2 x ULN (or INR > 1.5)	None	
If elevated at baseline: ALT/AST > 2 x baseline	For participants with Gilbert's syndrome: Doubling of direct bilirubin at baseline	None	
 Study drug can be restarted only if another etiology is identified and liver enzymes return to baseline.
If normal at baseline: ALT/AST > 3 x ULN	Normal or elevated	Severe fatigue, nausea, vomiting, right upper quadrant pain	
If elevated at baseline: ALT/AST > 2 x baseline			
Hy's Law cases:	
 - ALT or AST > 3 x ULN and TBL > 2 x ULN, without notable increase in ALP to > 2 x ULN, and - Absence of any alternative cause likely explaining the combination of increased ALT or AST and TBL (such as viral hepatitis A, B, C, or E); pre-existing acute liver disease; or another drug capable of causing the observed injury 		
 Interrupt study drug Report to Novartis as SAE Treat the condition and measure ALT, AST, ALP, GGT, TBIL, INR, albumin, CK, and GLDH at the frequency per Investigator's discretion

Table 16-2 Follow up requirements for isolated total bilirubin elevation

Criteria	Actions required	Follow-up monitoring
Total Bilirubin (isolated)		
>1.5 – 3.0 ULN	
 Repeat LFTs within 48-72 hours 	Monitor LFTs weekly until resolution to ≤ Grade 1 or to baseline
> 3 - 10 × ULN (in the absence of known Gilbert syndrome)	
 Interrupt treatment Repeat LFT within 48-72 hours Hospitalize if clinically appropriate Establish causality Record the AE and contributing factors (e.g. conmeds, med hx, lab) in the appropriate eCRFs 	Monitor LFTs weekly until resolution to ≤ Grade 1 or to baseline (ALT, AST, total bilirubin, Alb, PT/INR, ALP and GGT) Test for hemolysis (e.g. reticulocytes, haptoglobin, unconjugated [indirect] bilirubin)
> 10 x ULN	
 Discontinue the study treatment immediately Hospitalize the participant Establish causality Record the AE and contributing factors(e.g. conmeds, med hx, lab)in the appropriate eCRFs 	ALT, AST, total bilirubin, Alb, PT/INR, ALP and GGT until resolution* (frequency at investigator discretion)

* Resolution is defined as an outcome of one of the following: (1) return to baseline values, (2) stable values at three subsequent monitoring visits at least 2 weeks apart, (3) remain at elevated level after a maximum of 6 months, (4) liver transplantation, and (5) death.

For any AE potentially indicative of a liver toxicity, consider study drug interruption or discontinuation and hospitalization if clinically appropriate. Establish causality and record the AE and contributing factors in the appropriate eCRFs. Based on Investigator's discretion, investigation(s) for contributing factors for the liver event can include: Serology tests, imaging and pathology assessments, hepatologist's consultancy; obtaining more detailed history of symptoms and prior or concurrent diseases, history of concomitant drug use, exclusion of underlying liver disease.

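### Without symptoms or Gilbert's syndrome, Table 16-1 has no row for raised ALT/AST with bilirubin above 1 to 2 x ULN and INR at most 1.5 or unmeasured, so its required action lapses in that band

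*Protocol*

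**What the plan says.** Section 16.1 of the protocol opens with the statement "Tables below provide the clinically notable liver function test results and the required actions". Table 16-1 then sorts ALT/AST rises by total bilirubin (TBL) and liver symptoms. Under the block heading "ALT/AST increase without bilirubin increase" stand three rows for participants without symptoms:

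- above 3 x ULN (above 2 x baseline if raised at baseline): treatment continues, a liver panel including INR is drawn at 48-72 hours, and the cause is followed up;
- above 5 x ULN for over two weeks (above 3 x baseline for over two weeks if raised at baseline);
- "If normal at baseline: ALT/AST > 8 x ULN".

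All three require a normal TBL. The first two add an alternative for Gilbert's syndrome (no clinically significant change from baseline TBL). The third does not.

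In the bilirubin-increase block, the row for participants without symptoms has a TBL entry that begins "TBL > 2 x ULN (or INR > 1.5", with doubling of direct bilirubin as the Gilbert's criterion. The only row that accepts TBL at any level requires symptoms. The Hy's Law row needs "ALT or AST > 3 x ULN and TBL > 2 x ULN" and states interruption on its own line.

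Table 16-2 is titled "Follow up requirements for isolated total bilirubin elevation". Above 1.5 and up to 3.0 x ULN it asks the site to "Repeat LFTs within 48-72 hours" and then monitor weekly. Interruption starts above 3 x ULN. The text after it says that for an adverse event pointing to liver toxicity the investigator should "consider study drug interruption or discontinuation and hospitalization if clinically appropriate".

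**The concern.** A liver safety rule should not ask for less when bilirubin rises alongside transaminases. Read row by row, Table 16-1 does so in one band. The normal-bilirubin rows stop at ULN and the next symptom-free row begins above 2 x ULN, with nothing in between unless INR exceeds 1.5.

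INR does not reliably fill the hole. It is not in the routine chemistry panel (Table 8-4), and the 48-72 hour retest that includes it belongs to the rows this participant misses. The follow-up duty in Section 10.2.1 attaches to liver events defined in Tables 16-1 and 16-2, so a participant who matches no row does not clearly trigger it.

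At stake are a required interruption at the higher ALT/AST thresholds and a fixed early retest at the lowest one. The SAP shows that part of the band is of interest to the sponsor: Section 5.3.2 tabulates ALT or AST above 3 x ULN with TBL above 1.5 x ULN.

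**Working it through.** This is a check of table logic, and there is no planned figure to reproduce. Inputs are the Table 16-1 and 16-2 rows, the Table 8-1 visit days and the Table 8-4 panel.

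**Step 1: which action cell belongs to which row.** The action cells are displaced in the text available to me. I read the interrupt instruction as covering the sustained above-5 x and above-8 x rows and the bilirubin-increase rows, for three reasons:

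- Under continued treatment, the above-5 x and above-8 x rows would add nothing to the above-3 x row, which already captures them.
- The restart condition printed in the bilirubin-increase block presupposes interruption.
- The Hy's Law row states interruption explicitly.

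**Step 2: row walk.** Normal baseline ALT/AST, no symptoms, no Gilbert's syndrome, INR at most 1.5 or unmeasured. Values are multiples of ULN. Where two rows match, the stricter is shown.

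| ALT/AST | TBL 0.9 | TBL 1.1, 1.5, 1.6, 2.0 | TBL 2.1 |
|---|---|---|---|
| 4 | retest at 48-72 h | no row | interrupt |
| 6 for over two weeks | interrupt | no row | interrupt |
| 10 | interrupt | no row | interrupt |

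With INR 1.6, every point matches the INR row. With baseline ALT raised at 1.5 x ULN, the lowest threshold is 2 x 1.5 = 3.0 x ULN. An unsustained ALT of 9 x ULN then matches the retest row at TBL 0.9, no row at 1.2, 1.6 or 2.0, and the bilirubin-increase row at 2.1.

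**Step 3: does Table 16-2 close the gap?** Its scope is isolated bilirubin. Applied anyway, it asks for nothing at TBL 1.1 or 1.5, and for repeat tests plus weekly monitoring at 1.6 and 2.0. It requires no interruption anywhere up to 2.0. A participant with TBL 1.6 and normal ALT thus has a fixed retest, while one with TBL 1.6 and ALT 4 x ULN matches no row of Table 16-1.

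**Step 4: do other sections require interruption?** Section 6.6 lists events that may lead to interruption on the investigator's judgement. Section 10.2.1 asks for it to be considered if appropriate. The text after Table 16-2 also says consider. Section 9.1.1 makes discontinuation mandatory, but only once the investigator judges that there is a safety risk.

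**Step 5: outer bound on time to the next scheduled test.** Chemistry is drawn on days 28, 84, 168, 252 and 336. The gaps are 84 - 28 = 56 days, then 84 days three times (168 - 84, 252 - 168, 336 - 252). Doses strictly between draws fall on day 56; days 112 and 140; days 196 and 224; and days 280 and 308. That is 1, 2, 2 and 2 doses. The bound assumes that nobody orders an unscheduled test.

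**The case against.** The strongest reply is that other text covers these participants. Much of that stands:

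- Section 9.1.1 requires the investigator to stop treatment if continuing would harm the participant's well-being, and lists any situation carrying a safety risk among the reasons for mandatory discontinuation.
- Section 8.4.1 requires every abnormal result to be evaluated as a possible adverse event and recommends repeat testing of laboratory events until they normalise.
- ALT above 5 to 20 x ULN is Grade 3 in SAP Table 5-3, and Section 10.1.1 defines notable laboratory findings by CTCAE. ALT of 8 to 10 x ULN would very likely become an adverse event, with follow-up to resolution.

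A reader might infer from Step 5 that a participant could go 56 or 84 days untested. The documents do not support that as an expectation, given the recommended repeat testing. The sustained above-5 x case fits it especially poorly: showing over two weeks' duration needs at least two draws, and if TBL was normal at the first, the above-3 x row already required a retest with INR. The bound mainly fits a participant whose TBL is already raised at the draw that first shows the ALT/AST rise.

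Two further points are fair. The interrupt, no row, interrupt contrast rests on the reading in Step 1, although the missing row and the lost retest at above 3 x ULN do not. And SAP Section 5.3.2 is a tabulation list that also counts TBL above 1 x ULN alone, so it does not set an action standard.

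What the objection does not answer is why interruption is mandatory at normal bilirubin, where the same discretion exists, and not when bilirubin is also raised.

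**Conclusion.** The gap is real: one TBL band, above 1 to 2 x ULN, is missing for all three symptom-free ALT/AST thresholds when INR is at most 1.5 or unmeasured and the participant does not have Gilbert's syndrome. At the two higher thresholds a required interruption becomes a matter of judgement, given the Step 1 reading. At the lowest threshold no interruption is lost, but the fixed 48-72 hour retest with INR is.

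The reach is narrow. The documents give no incidence, the study enrols about 100 participants, and exclusion criterion 16 removes chronic liver or biliary disease, so I expect few cases. Investigators would probably act anyway.

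A reader might infer that the protocol leaves these participants unprotected, or tells sites to keep dosing. It does neither: no row applies, and the duties in Sections 8.4.1, 9.1.1 and 10.1.1 continue. No efficacy analysis is affected. This is a defective safety rule that is cheap to correct, and it does not threaten the study's conclusions.

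**What to change.** Amend Table 16-1 as follows.

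- (a) In the sustained above-5 x ULN (above 3 x baseline) row and the above-8 x ULN row, extend the TBL entry from normal to normal or elevated up to 2 x ULN, with interruption as the action.
- (b) For ALT/AST above 3 x ULN (above 2 x baseline) with TBL above ULN to 2 x ULN, add a separate row: retest at 48-72 hours including INR, causality follow-up, and interruption to be considered. Simply widening the existing row would be worse, because it would write in continued treatment for a case such as ALT 4 x ULN with TBL 1.9 x ULN, where interruption is now at least to be considered.
- (c) For Gilbert's syndrome, make the sustained above-5 x and the above-8 x rows apply at any TBL that does not meet the doubling-of-direct-bilirubin criterion, and apply row (b) when TBL has changed significantly without that doubling. Otherwise such a participant still matches no symptom-free row in these blocks unless INR exceeds 1.5.
- (d) Reword the block heading so that it covers bilirubin up to 2 x ULN.

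On the Step 2 grid, ALT 6 x ULN for over two weeks and ALT 10 x ULN then lead to interruption at every TBL value. ALT 4 x ULN moves from retest, to retest with interruption considered, to interruption.

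The cost is an edit to one appendix table, a few extra central-laboratory retests and rare extra interruptions. No new type of assessment is needed.

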16.2 Appendix 2: Specific Renal Alert Criteria and Actions and Event Follow-up

Table 16-3 Specific Renal Alert Criteria and Actions

Serum Event	Action
Serum creatinine (sCr) increase $\geq 25\%$ compared to baseline during normal hydration status	
 Confirm 25% increase ≥ 24 hours but within 5 days Consider causes and possible interventions (including study drug interruption)
Urine Event	Action
Urine protein-creatinine ratio(PCR) $\geq 1\text{g/g}$ or $\geq 100\text{ mg/mmol}$ OR New onset dipstick proteinuria $\geq 3+$ OR New onset dipstick hematuria $\geq 3+$ (after excluding menstruation, urinary tract infection, extreme exercise, or trauma)	
Follow-up of Renal Events 
 Document contributing factors in the eCRF: co-medication, other comorbid conditions, and additional diagnostic procedures Monitor participant at Investigator's discretion 	

*urine PCR can be used as a follow-up of a positive urine dipstick proteinuria.

16.3 Appendix 3: The 2017 McDonald criteria for diagnosis of multiple sclerosis in patients with an attack at onset

Table 16-4 2017 McDonald criteria for diagnosis of multiple sclerosis in patients with an attack at onset

Number of lesions with objective clinical evidence		Additional data needed for a diagnosis of multiple sclerosis
≥ 2 clinical attacks	≥ 2	None*
≥ 2 clinical attacks	1 (as well as clear-cut historical evidence of a previous attack involving a lesion in a distinct anatomical location)	None*
≥ 2 clinical attacks	1	Dissemination in space demonstrated by an additional clinical attack implicating a different CNS site or by MRI
1 clinical attack	≥ 2	Dissemination in time demonstrated by an additional clinical attack or by MRI OR demonstration of CSF-specific oligoclonal bands
1 clinical attack	1	Dissemination in space demonstrated by an additional clinical attack implicating a different CNS site or by MRI AND Dissemination in time demonstrated by an additional clinical attack or by

		MRI OR demonstration of CSF-specific oligoclonal bands¶

If the 2017 McDonald Criteria are fulfilled and there is no better explanation for the clinical presentation, the diagnosis is multiple sclerosis. If multiple sclerosis is suspected by virtue of a clinically isolated syndrome but the 2017 McDonald Criteria are not completely met, the diagnosis is possible multiple sclerosis. If another diagnosis arises during the evaluation that better explains the clinical presentation, the diagnosis is not multiple sclerosis.
 
*No additional tests are required to demonstrate dissemination in space and time. However, unless MRI is not possible, brain MRI should be obtained in all patients in whom the diagnosis of multiple sclerosis is being considered. In addition, spinal cord MRI or CSF examination should be considered in patients with insufficient clinical and MRI evidence supporting multiple sclerosis, with a presentation other than a typical clinically isolated syndrome, or with atypical features. If imaging or other tests (eg, CSF) are undertaken and are negative, caution needs to be taken before making a diagnosis of multiple sclerosis, and alternative diagnoses should be considered. †Clinical diagnosis based on objective clinical findings for two attacks is most secure. Reasonable historical evidence for one past attack, in the absence of documented objective neurological findings, can include historical events with symptoms and evolution characteristic for a previous inflammatory demyelinating attack; at least one attack, however, must be supported by objective findings. In the absence of residual objective evidence, caution is needed.
 
¶The presence of CSF-specific oligoclonal bands does not demonstrate dissemination in time per se but can substitute for the requirement for demonstration of this measure.
		

16.4 Appendix 4: Guidance on safety monitoring and immunization

16.4.1 Guidance on monitoring of participants with symptoms of neurological deterioration suggestive of PML

Should a participant develop any unexpected neurological or psychiatric symptom/signs in the opinion of Investigator (e.g. cognitive deficit, behavioral changes, cortical visual disturbances or any other neurological cortical symptoms/signs any symptom/sign suggestive of an increase of intracranial pressure) or accelerated neurological deterioration, the Investigator should schedule a complete physical and neurological examination and an MRI as soon as possible before beginning any steroid treatment. Conventional MRI, as defined in the protocol, as well as additional scanning such as Fluid-attenuated Inversion Recovery (FLAIR) and Diffusion weighted imaging (DWI) sequences should be performed to aid in differential diagnosis. The MRI must be evaluated by the local neuroradiologist. The Investigator will contact the Medical Advisor at Novartis to discuss findings and diagnostic possibilities as soon as possible. A copy of the unscheduled MRI should be sent to the MRI Evaluation Center designated by Novartis as soon as possible. SAEs need to be reported and filed as appropriate. If the MRI shows (new) lesions consistent with a MS relapse assessment and treatment of the relapse will be performed as described in the protocol (Section 6.2.3). In case of new findings in the MRI images, in comparison with the previously available MRI, which are not compatible with lesions consistent with a MS relapse, the study drug will be interrupted and other diagnostic evaluations need to be performed at the discretion of the Investigator. If new lesions are detected on the MRI, which may be infectious in origin, it is recommended to collect a cerebrospinal fluid (CSF) sample if indicated. Analysis of the CSF sample including cellular, biochemical, PCR, and microbiological analysis (e.g. herpes virus, JC virus, cryptococcus) to confirm/exclude an infection should be performed. In the event of suspected CNS infection (PML), a CSF aliquot should be sent to a qualified laboratory (designated by Novartis) for confirmatory testing. Only after the evaluations have excluded diagnoses other than MS and

after discussion with the Medical Advisor at Novartis and a Global Study Team member, the study drug may be restarted.

